10.2 Systemic cytokines and growth factor assays

Approximately 10ml of blood will be collected in a tube that does not contain EDTA (silicone-coated, red-top tube) at baseline, 4 weeks, and 8 weeks (if the patient remains on MGE treatment) to measure cytokines and growth factors (including but not limited to TNF α , IL6, IL6R, IL8, IL1 α , IL1 β , IGF-1, VEGF), using the Cira multiplex solid phase immunoassay platform from Aushon and the Human Cytokine 2 and Angiogenesis Factor 1 Arrays²⁷⁻²⁹, as well as individual ELISA's for CRP, TGF β 1, IGF-1. The blood will be allowed to clot. Serum will be collected and samples will be stored at -80°C for an indefinite period of time.

Forms/Data collected	Collection Time Point	Data Management
Informed consent document	Pre-study	ORIS/WakeOne
Protocol Registration & Race Verification Forms	Pre-study	ORIS
Adverse Event Log (Toxicity including CBC with	Each monthly clinic visit	ORIS (labs to be
differential, platelets, serum chemistries)		pulled from EPIC)
Labs (CBC with differential, platelets, serum	Baseline and monthly	ORIS (labs to be
chemistries)	clinic visit	pulled from EPIC)
Treatment Response Evaluation	Monthly clinic visit	REDCap
End of Treatment Evaluation of Best Response	Off-study	REDCap
Baseline Data Collection Form	Baseline	REDCap
Follow-up Data Collection Form	Monthly clinic visit	REDCap
Correlative Research Labs Data Collection Form	Baseline, week 4, week 8	REDCap
Telephone Follow-up Form	Weeks 2 & 6	REDCap
FACT-G	Baseline and monthly	REDCap
PROMIS-Fatigue	Baseline and monthly	REDCap
Daily Pill Dairy	Monthly clinic visit	REDCap
Off Study Documentation Form	Off-study	REDCap
Follow-Up Form for Survival	Every 6 weeks	ORIS

11.0 Data Management

12.0 Statistical Considerations

12.1 Analysis of Primary Objective

The primary objective of determining the safety and MTD of MGE will be completed by monitoring toxicities and using the dose escalation plan detailed above.

To determine the maximum tolerated dose (MTD) of MGE in patients with metastatic cancer, we will use a standard 3+3 Phase 1 dose escalation statistical design. All MGE dose escalations conducted will be escalated according to the dose escalation scheme (see Section 6.2). The number of patients in each cohort will be 3. If no patients in any cohort develop a dose-limiting toxicity (DLT), dose escalation will continue in cohorts of 3 patients up to the maximum dose. However, if a DLT is observed in 1 of 3 patients at any dose level, the cohort of that dose level will be expanded to a maximum of 6 patients. If 1 of the 6 patients has a DLT, the dose escalation procedure will continue in 3 patients for each subsequent cohort. However, once a DLT is observed in a total of 2 patients at any dose level. dosing of MGE in patients at that dose level will stop immediately, even though the total number of patients at the last cohort may be as few as 2. Dose escalation is considered to be complete. The dose level that induces a DLT in 2 or more patients is considered to be above MTD, and the dose level immediately below the dose level that induced a DLT in ≥2 patients is considered the MTD for MGE if ≤1 participants of 6 patients at that level have a DLT.

In the event that the MTD is not observed after the 5 dose levels listed in Section 6.2 have been tested, the investigators will consider stopping additional dose escalation. The decision will be based on the actual dose level tested, the extent of anti-tumor efficacy observed, and the type of toxicity observed, etc.

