At the time of sacrifice, various organs (heart, lung, liver, kidney, spleen and brain) were removed and weighed and the organ weights of mice treated with each dose of MGE were compared to the untreated control group. A portion of each organ was fixed in formalin, sectioned and stained with H & E. for assessment by a veterinary pathologist. In addition. the heart and kidney were assessed by echocardiography and radioimmunoassay of urinary proteins, respectively, as a further measure of heart and renal function. There was no difference in the weight or structure of the hearts of mice treated with increasing doses of MGE. Cardiac parameters including ejection fraction, fractional shortening, cardiac output, stroke volume and heart rate were all similar in mice treated with MGE compared to untreated Control mice. There was no difference in the weight or structure of the lungs of mice treated with MGE compared to the untreated control mice. The weight of the livers of mice treated with the two lowest MGE (0.25 and 0.5 mg phenolics/mouse/day) and the highest MGE (2.0 mg phenolics/mouse/day) concentrations were no different than the weight of the livers of the untreated mice. However, the weight of the livers of mice in the 1.0 mg phenolics/mouse/day) were slightly increased compared to the control. Spleen weight of mice treated with MGE was not significantly different than untreated control mice and the spleens of mice were generally within normal limits with one mouse in the highest MGE treatment group having some extra medullary hematopoiesis. The weight of the brains of mice treated with MGE was not significantly different than untreated mice. The brains were subdivided into four regions—cortex, cerebellum, hypothalamus and brainstem. All brain regions examined were within normal limits.

Conclusions from toxicity studies and corresponding clinical doses:

Little toxicity was observed at any of the doses tested. Therefore, the level of phenolics used to treat the mice suggests that this level of phenolics and corresponding numbers of capsules will likely be tolerated by patients. However, based upon patient compliance, a recommended dose range for patients would include 2, 4, 6, 8 and 10 capsules/day (corresponding to approximately 5, 9, 14, 18 and 23 mg phenolics/kg/day).

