1.3 Clinical Studies

Muscadine grape skin extract has been evaluated in clinical trials to a limited extent in the setting of cardiovascular disease²³ and diabetes.²⁴ In a randomized, double-blind, placebo-controlled crossover trial, 50 adults with coronary disease or \geq 1 cardiac risk factor received muscadine grape seed supplementation (1300 mg daily) and placebo for 4 weeks each, with a 4-week washout, and no adverse events were reported.²³ Similarly, a randomized study of non-diabetic and type 2 diabetic participants using 150 mL of muscadine grape juice, muscadine grape wine, and dealcoholized muscadine grape wine over a 28-day period had no adverse events reported.²⁴

A muscadine grape product has also been examined in a phase 1/2 trial of men with biochemically recurrent prostate cancer.²⁵ The phase 1 portion of the study evaluated increasing doses of pulverized muscadine grape skin in a product called MPX (Muscadine Naturals Inc, Clemmons NC) in cohorts of two patients, with six patients at the highest dose of 4,000 mg (n=14). Dose selection was based on unpublished preclinical work in animal studies. Four patients experienced adverse gastrointestinal symptoms possibly related to the study agent, including grade 1 flatulence, grade 1 soft stools, and grade 1 burping. No other related adverse events were reported and one patient reported improvement of chronic constipation. Six of the 14 patients came off study for disease progression (five metastatic, one rising PSA) after exposure for a median of 15 months.

One patient came off study for myasthenia gravis that was unrelated to treatment. Seven patients remained on the study. The lack of dose-limiting toxicities led to the selection of 4,000 mg/d as the highest dose for further study. Median within-patient PSA doubling time increased by 5.3 months (non-significant, P=0.17). Based on the favorable safety profile and a possible lengthening of PSA doubling time, the phase 2 portion of this study was expanded to 125 patients randomized to placebo, 500 mg/d, or 4000 mg/d MPX arms. Recruitment was completed in October 2014 with results pending.

In summary, muscadine grape products have shown anti-cancer activity in preclinical models and have demonstrated a favorable safety profile in preclinical and clinical studies. This Phase 1 study using MGE represents an opportunity to translate promising preclinical data supporting the anti-cancer properties of a natural product into clinical trials.

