6.2.1 Definition of Dose-Limiting Toxicity (DLT)

Dose-limiting toxicity (DLT) will be defined as grade 3 gastrointestinal side effects attributable to treatment or any grade 4 or 5 adverse event attributable to treatment as per the Common Terminology Criteria for Adverse Events (CTCAE) 4.0 criteria. Any adverse event attributable to treatment and resulting in permanent discontinuation of MGE will be considered a DLT. Toxicity will be assessed at 4 weeks. Any DLTs that occur 1 day (day 29) after the 4 week period will be evaluated and considered as potentially attributable to the administration of MGE during the first 4 weeks. The washout period for this drug is 24 hours. Dose escalation will proceed within each cohort as follows:

Number of Patients with DLT at a Given Dose Level	Escalation Decision Rule		
0 out of 3	Enter 3 patients at the next dose level.		
> 2	Dose escalation will be stopped. This dose level will be declared the maximally administered dose (highest dose administered). Three (3) additional patients will be entered at the next lowest dose level if only 3 patients were treated previously at that dose.		
1 out of 3	 Enter at least 3 more patients at this dose level. If 0 of these 3 patients experiences DLT, proceed to the next dose level. If 1 or more of this group suffer DLT, then dose escalation is stopped, and this dose is declared the maximally administered dose. Three (3) additional patients will be entered at the next lowest dose level if only 3 patients were treated previously at that dose. 		
≤1 out of 6 at highest dose level below the maximally administered dose	This is generally the recommended phase 2 dose (Maximum Tolerated Dose [MTD]). At least 6 patients must be entered at the recommended phase 2 dose.		

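### If the top dose level clears, no rule names a dose and no step fills it from three patients to six; separately, the toxicity tables omit dose level and some grade 3 events.

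*Combined protocol and SAP*

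**What the plan says.** Section 6.2 lists five levels, from 1 to 5 pills twice daily, and no sixth. Under 12.1, if no DLTs occur, "dose escalation will continue in cohorts of 3 patients up to the maximum dose". A level is expanded to six only after 1 DLT in 3, or when the level above it has been stopped.

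Both sections define the MTD from above. In 12.1, "The dose level that induces a DLT in 2 or more patients is considered to be above MTD", and the MTD is the level immediately beneath it, provided that level has no more than 1 DLT in 6. The last row of the 6.2.1 table applies the same logic and adds: "At least 6 patients must be entered at the recommended phase 2 dose".

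If five levels are tested without an MTD, 12.1 says "the investigators will consider stopping additional dose escalation". It continues: "The decision will be based on the actual dose level tested, the extent of anti-tumor efficacy observed, and the type of toxicity observed, etc".

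On reporting, 12.2.1 plans frequency tables for the whole study and by week. They cover expected toxicities, laboratory toxicities, gastrointestinal events of grade 3 or above, and anything of grade 4 or above. Dose level is not a table dimension there, although adherence is summarised per dose level (12.2.7).

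**The concern.** Objective 2.1.1 is safety and the MTD, yet the plan has no stated conclusion for a path that its own background makes plausible. The dose range was not set to reach toxicity: "based upon patient compliance, a recommended dose range for patients would include 2, 4, 6, 8 and 10 capsules/day" (1.2). The mouse study behind it saw little toxicity at doses that the protocol scales to as many as 42 capsules a day, apart from a small weight loss at the top dose. Section 8.1 expects few and mild adverse events. The earlier phase 1 trial of a different muscadine product, described in 1.3, saw no DLTs; it placed six patients at its highest dose.

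If level 5 clears, the 0/3 and 1/6 rules both point to a next level that is not listed, and 12.1 addresses whether to go on escalating, not which dose to report. On the 0/3 path the study could stop with three patients at its highest dose and its six-patient requirement not carried out.

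The second matter is smaller. Apart from the DLT counts used for escalation, no planned summary shows toxicity by dose over a five-fold range (2 to 10 pills a day). A grade 3 event that is unexpected, non-gastrointestinal and non-laboratory falls in none of the four categories. That can include a DLT, since "Any adverse event attributable to treatment and resulting in permanent discontinuation of MGE will be considered a DLT" (6.2.1).

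**Working it through.** **The plan's own figures.** The maximum of 30 (12.3) is 5 levels × 6 patients. The minimum of 2 is two DLTs in the first two patients at level 1. At 2 patients a month, 30/2 = 15 months, which agrees with the stated under 16 (12.4). So the maximum already allows six patients at level 5.

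**The rules at level 5.**

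- 0/3: enter three at the next level. None is listed.
- 1/3, then 0 of 3 more: proceed to the next level. None is listed.
- 2 or more DLTs: level 4 is considered, and filled to six if it has only three. This case is covered.

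**How often level 5 clears.** The documents give no DLT rate for MGE, so every rate p here is an assumption. With q = 1 − p:

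- P(clear a level) = q³ + 3pq⁵.
- P(level 5 clears at 0/3) = product of the clearance probabilities of levels 1 to 4, times q₅³.
- P(level 5 clears at 1/6) = the same product, times 3p₅q₅⁵.

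Example at a constant 10%: clearance is 0.729 + 0.177 = 0.906. Then 0.906⁴ = 0.674, and 0.674 × 0.729 = 0.491.

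| Assumed DLT rate, levels 1 to 5 | Clears at 0/3 | Clears at 1/6 | Either |
|---|---|---|---|
| 2% constant | 0.924 | 0.053 | 0.98 |
| 5% constant | 0.770 | 0.104 | 0.87 |
| 10% constant | 0.491 | 0.119 | 0.61 |
| 15% constant | 0.269 | 0.088 | 0.36 |
| 20% constant | 0.129 | 0.050 | 0.18 |
| 2-5-8-12-18% | 0.436 | 0.158 | 0.59 |
| 5-10-15-20-25% | 0.215 | 0.091 | 0.31 |
| 5-10-20-30-40% | 0.067 | 0.029 | 0.10 |

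The earlier trial does not narrow this range much. No DLTs in 14 patients, on another product, has a two-sided exact 95% upper end of 1 − 0.025^(1/14) = 23%.

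**What three or six patients show.** These are upper ends of two-sided exact (Clopper-Pearson) 95% intervals, with one-sided 95% limits in brackets:

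- 0/3: 1 − 0.025^(1/3) = 71% (63%)
- 0/6: 1 − 0.025^(1/6) = 46% (39%)
- 1/6: 97.5th percentile of Beta(2, 5) = 64% (58%)

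**What filling to six changes.** After 0/3, level 5 would stay clear with at most 1 DLT in the next 3, so clearance by this path is q³(q³ + 3pq²) instead of q³.

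- p = 30%: 0.343 × 0.784 = 0.269, down from 0.343. Counting both paths, 0.42, down from 0.49.
- p = 40%: 0.216 × 0.648 = 0.140, down from 0.216.

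The chance that the three added patients bring 2 or more DLTs is 1 − q³ − 3pq² = 0.03, 0.10 and 0.22 at p = 10%, 20% and 30%.

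**The case against.** The strongest reply is that the six-patient safeguard is already written. The sentence in 6.2.1 is unqualified, although it sits in the row for the level beneath a failed one. A reader might infer that the plan permits level 5 to be recommended on three patients. Read plainly, that sentence forbids it. The principle is present; the step that carries it out at the top level is missing.

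A reader might also infer that the trial must end when level 5 clears at 0/3. The text does not say so. Considering whether to stop leaves further escalation open, so the probabilities above are for level 5 clearing, not for the trial ending there. Investigator judgement at the end of a phase 1 range is a legitimate choice, and 12.1 does anticipate the case and names three criteria. What remains faulty is that the list is open-ended and that no dose results from it.

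The statistical benefit of the extra patients is indeed small, and the frequency of the gap depends wholly on assumed rates.

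On the tables, a reader might infer that nobody could tell which events occurred at the dose in question. That goes too far. DLTs are counted by level, every patient's dose is assigned at registration, adverse events are logged, and 12.2.1 does not forbid further tables. A grade 3 DLT through discontinuation still enters the escalation decision. The list of expected events in 8.1 is also illustrative: its five named events are all gastrointestinal, but others might count as expected. What stands is that no planned summary other than the DLT counts shows toxicity by dose, and that the stated categories leave a gap.

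**Conclusion.** Both points hold and should be corrected. First, if level 5 clears by either path, neither MTD rule yields a dose, and after 0/3 nothing in the escalation scheme implements the protocol's own six-patient minimum. The chance of clearing at 0/3 runs from 0.07 to 0.92 over the assumed curves. No single value should be quoted as the likelihood, though the sponsor's expectation of little toxicity points towards the upper part of that range. These figures take patients as independent and evaluable. The reason to act is a conclusion fixed in advance and consistency with the protocol's own standard; better screening of a toxic dose is a minor gain. The rules for levels below the top are not in question here.

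Second, and minor, the toxicity summary omits dose level and one class of grade 3 event. This is a reporting gap and does not affect the escalation decisions.

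**What to change.** In 6.2.1 and 12.1, state that:

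- if level 5 clears at 0/3, it is filled to six before it can be recommended;
- with 1 or fewer DLTs in 6, by either path, the report will read *MTD not reached; level 5 is the highest dose tested and is eligible as the recommended phase 2 dose*, with the exact two-sided 95% interval for the DLT rate;
- with 2 or more DLTs, the existing rule applies to level 4;
- investigators may still choose a lower dose, on a closed list of criteria;
- any dose above level 5 needs an amendment.

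Cost on the path where every level is 0/3: 18 patients instead of 5 × 3 = 15, or 21 if the expanded level 5 fails and level 4 must also be filled. At 2 patients a month this is 3/2 = 1.5 to 6/2 = 3 months of accrual, plus one or two 4-week DLT windows. Any further step down stays within 5 × 6 = 30 evaluable patients. Replacements for inevaluable patients (7.1) come on top, as they do now.

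In 12.2.1, tabulate all adverse events by dose level, CTCAE grade and attribution, with DLT counts and exact intervals per level. Label these tables descriptive, since three to six patients per level cannot establish a trend. They use the adverse event log already kept and need no new data.

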12.2 Analysis of Secondary Objective

12.2.1 To monitor toxicity at 4, 8, and every 4 weeks thereafter on MGE

To analyze objective 2.1.1, we will summarize any expected toxicities, any laboratory based toxicities, and any grade 3 or higher gastrointestinal toxicities and any grade 4 or higher toxicities using frequency tables overall and by week.

12.2.2 To evaluate change in phenolic levels (total and component, blood and urine) from baseline to 4 and 8 weeks

To analyze objective 2.2.2, we will fit a mixed model ANOVA model with phenolic level as the outcome and time (baseline, 4, and 8 weeks) as a fixed effect and subject as a random effect. We will use contrasts to estimate the changes from baseline to week 4 and week 8.

12.2.3 To evaluate change in serum cytokines and growth factors from baseline to 4 and 8 weeks on MGE

To analyze objective 2.2.3, we will fit a mixed model ANOVA model with the outcome of interest (cytokine or growth factor) as the outcome and time (baseline, 4, and 8 weeks) as a fixed effect and subject as a random effect.

We will use contrasts to estimate the changes from baseline to week 4 and week 8.

12.2.4 To observe the response rate of MGE in patients with metastatic cancer.

To analyze objective 2.2.4, we will characterize response at 8 weeks using frequency table. We will also characterize the best response at the end of treatment with MGE using a frequency table.

12.2.5 To assess overall and progression-free survival in patients with metastatic cancer receiving MGE.

To analyze objective 2.2.5, we will summarize overall survival and progression-free survival using the Kaplan-Meier method. We will calculate median survival rates and associated 95% confidence intervals. Patients will be censored at date of last contact.

12.2.6 To assess global quality of life and fatigue in cancer patients taking MGE.

Quality of Life and fatigue will be monitored every 4 weeks until the end of the study. To analyze objective 2.2.6, we will fit a mixed model ANOVA model with phenolic level as the outcome and time (baseline, every 4 weeks) as a fixed effect and subject as a random effect. We will use contrasts to estimate the changes from baseline to each follow-up time period.

12.2.7 To assess adherence to MGE treatment.

To analyze objective 2.2.7, we will summarize the percent of pills taken at the end of every 4 week period i using the formula:

Percent of pills taken_i =
$$\frac{(Dose \ Level \ \times \ 7 \ \times \ 4)_i - Pill \ Count_i}{(Dose \ Level \ \times \ 7 \ \times \ 4)_i}$$

In the formula above, pill count will be calculated from counting the number of pills returned as well as by summarizing the patient's pill diary. The percent of pills taken will be summarized by dose level using the mean and 95% confidence interval.

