5.2 Secondary Outcomes

- 5.2.1 Adverse events/toxicity at weeks 4, 8 and every 4 weeks thereafter if remain on treatment
- 5.2.2 Identification of measured phenolic levels (total and component phenolics) at baseline,4, and 8 weeks
- 5.2.3 Evaluate change in systemic cytokines, growth factors from baseline to 4 and 8 weeks including but not limited to: TNF α , IL6, IL6R, IL8, IL1 α , IL1 β , IGF-1, VEGF
- 5.2.4 Overall response rate (CR, PR, and SD) at 8 weeks.
- 5.2.5 PFS and OS in patients with metastatic cancer receiving MGE under the proposed regimen.
- 5.2.6 Quality of life in cancer patients taking MGE using the Functional Assessment of Cancer Therapy–General (FACT-G) measure and fatigue, as measured by the PROMIS Fatigue-Short Form.
- 5.2.7 Adherence to MGE treatment, as assessed by patient-reported medication logs and pill count every 4 weeks while on treatment.

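### Section 12.2.1 plans no toxicity table by dose level and no table for grade 3 events that are neither gastrointestinal nor laboratory-based

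*Combined protocol and SAP*

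**What the plan says.** Section 12.2.1 opens "To analyze objective 2.1.1, we will summarize any expected toxicities, any laboratory based toxicities" and completes the list with "any grade 3 or higher gastrointestinal toxicities and any grade 4 or higher toxicities using frequency tables overall and by week". That makes four categories and two layouts; dose level is not among the layouts. The five expected toxicities named in section 8.1 are all gastrointestinal (GI).

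The outcome being analysed is broader. Section 5.2.1 gives it as "Adverse events/toxicity at weeks 4, 8 and every 4 weeks thereafter if remain on treatment", with no limit on type or grade, and objective 2.1.1 asks for safety as well as the MTD.

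The DLT definition in section 6.2.1 begins "Dose-limiting toxicity (DLT) will be defined as grade 3 gastrointestinal side effects attributable to treatment or" and goes on to attributable grade 4 or 5 events of any kind. It then adds: "Any adverse event attributable to treatment and resulting in permanent discontinuation of MGE will be considered a DLT". Toxicity is assessed at 4 weeks, with day 29 allowed for. Under section 12.1 these counts drive escalation level by level: "If no patients in any cohort develop a dose-limiting toxicity (DLT), dose escalation will continue in cohorts of 3 patients".

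Two other places bear on dose. If no MTD is seen after level 5, section 12.1 says of any further escalation: "The decision will be based on the actual dose level tested, the extent of anti-tumor efficacy observed, and the type of toxicity observed, etc". For adherence, section 12.2.7 does specify a by-dose display: "The percent of pills taken will be summarized by dose level using the mean and 95% confidence interval".

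**The concern.** The reader of a dose-finding trial needs to see toxicity against dose. Here the only dose-specific toxicity result is the DLT count, which is narrow by design and closes at about 4 weeks. Everything else is pooled over doses, and one class of severe event is in no table.

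Take an attributable grade 3 rash or bleed in a patient who continues on MGE. It is not a DLT, because it is not GI, is below grade 4 and did not end treatment. It is not in the section 12.2.1 list either. Such events are not far-fetched for this protocol: section 6.4 asks for an INR check in warfarin users, and section 3.2.3 excludes patients with allergy to similar compounds.

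A level could therefore be reported as free of DLTs with no planned output showing the other severe events there. The investigators would also reach the decision after level 5 without a planned display of the dose-by-type information that section 12.1 tells them to use.

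**Working it through.** **Inputs.** Five dose levels (section 6.2); 3 patients per level, expanded to at most 6 (section 12.1); four table categories (section 12.2.1); the expected list (section 8.1); the DLT definition (section 6.2.1).

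**The plan's own figure.** 5 levels × 6 patients = 30, which agrees with the maximum enrolment in section 12.3. Each level therefore holds 3 patients, or 6 if expanded.

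**Which events have a table.** Each CTCAE grade is set against event type, using the section 12.2.1 list as written:

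| Grade | Expected (all GI) | Other GI | Laboratory | Neither GI nor laboratory |
|---|---|---|---|---|
| 1 | yes | no | yes | no |
| 2 | yes | no | yes | no |
| 3 | yes | yes | yes | **no** |
| 4 | yes | yes | yes | yes |
| 5 | yes | yes | yes | yes |

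Of 5 × 4 = 20 cells, 5 have no table. Of the 3 × 4 = 12 cells at grade 3 or above, 1 has none: grade 3, neither GI nor laboratory. An event in that cell reaches the DLT count only if it is attributable and ends treatment for good. Grade 3 laboratory events have a table but enter the DLT count only on that same condition.

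**What is shown by dose.** Adherence is (section 12.2.7). DLTs are, through the 3+3 rule. No section adds a by-dose table of other toxicity. The by-week layout is no substitute, because patients at every level contribute to the same study weeks.

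**What pooling hides.** Suppose all five levels pass on 0 of 3, giving 5 × 3 = 15 patients, and 3 patients have the same toxicity. The overall line is 3/15 = 20%. The top level may have contributed 0, 1, 2 or 3 of them, with the other 3, 2, 1 or 0 at lower levels, and the line does not change.

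This example has limits. With no DLT at any level, the three events cannot be, within the 4-week window, attributable grade 3 GI events, attributable grade 4 or 5 events, or attributable events that ended treatment. They could be grade 1 or 2 expected events, laboratory toxicities up to grade 3, events judged not attributable, or events after the window.

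**Late events.** Section 6.5 lets treatment run until progression or another stopping reason, and the section 6.1 schedule evaluates adverse events every 4 weeks. An attributable grade 3 GI or grade 4 event at week 8 has a place in the section 12.2.1 tables, but only pooled over doses. It comes after the 4-week assessment on which escalation rests.

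No probability is attached to any of this. The documents give no rate for grade 3 non-GI events and no share of them that would end treatment.

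**The case against.** The strongest reply is that nothing is lost. Adverse events are reviewed at each clinic visit (section 6.3.2.2) and entered in an adverse event log, with grade and attribution recorded under section 8.2. The dose is assigned at registration (section 4.0). Cohorts enter dose by dose, with at most 30 patients, so the investigators know the dose behind every event. Section 12.2.1 does not forbid further tables.

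This is right about data collection, and it limits the point to the planned analysis. It does not make the planned output adequate: the section names a list and a layout, and following them exactly omits dose and one class of severe event. The other oversight routes do not supply a table. Under section 8.3 the safety committee requires reports of unexpected grade 4 and all grade 5 serious events, so grade 3 is not routed there. IRB reporting under section 8.4 feeds no analysis.

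A reader might infer that the DLT definition is too narrow and should count every attributable grade 3 event. The documents do not establish that. Every expected event named is GI, and the phase 1 study in prostate cancer summarised in section 1.3 reported only grade 1 GI events as possibly related. Dose changes are not allowed (section 6.2.2), so an attributable event that forces a permanent stop is already a DLT. The narrow definition may well be deliberate.

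A reader might also picture patients held for a grade 3 event and then resumed in month 1. Section 6.2.2 allows a hold of up to 7 days but points to section 6.5.1, whose first-month text concerns misses unrelated to toxicity. That route is unclear, and the point does not need it: a patient who simply continues is enough.

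**Conclusion.** The point holds as a gap in the planned toxicity tables. One of the 12 grade-by-type cells at grade 3 or above has no table, and neither do four cells at grades 1 and 2. Apart from DLT counts in the 4-week window, no toxicity is shown by dose level. This falls short of the unrestricted outcome in section 5.2.1, the safety part of objective 2.1.1, and the use that section 12.1 makes of dose and type of toxicity.

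Two assumptions carry this. The section 12.2.1 list is taken as complete, and the expected list in section 8.1 is taken as the events it names, although its wording does not formally close it. Section 12.2.1 cites objective 2.1.1 where its heading matches 2.2.1; the conclusion is the same under either.

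The documents do not support saying that events go unrecorded, that escalation or the MTD would be wrong, or that a given share of levels would carry an unseen event. This is a cheap improvement to the analysis plan, with no change to the design.

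**What to change.** Replace the sentence in section 12.2.1 with:

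> All adverse events will be tabulated by CTCAE term, maximum grade and attribution, by dose level as well as overall and by week, with all grade 3 or higher events in any organ system shown separately.

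This fills all five empty cells, not only the grade 3 one, and gives the decision after level 5 the display it needs. Leave the DLT definition and the 3+3 rule alone. Listing attributable grade 3 events that were not DLTs beside the DLT count at each escalation decision is optional. The plan has no rule for acting on such a count, and none is proposed here.

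The cost is a little extra tabulation from data already collected, with no added patients, visits or tests. With 3 to 6 patients per level, the by-dose columns are descriptive and should carry no tests or claims of trend.
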